8.4 Pharmacokinetics

Blood will be collected in the contralateral arm that study drug was administered for the purpose of PK analysis for subjects enrolled in Groups 10 and 11 at the timepoints described below:

- Within 15 minutes prior to administration of Tc 99m tilmanocept
- Immediately following administration of Tc 99m Tilmanocept (00:00-00:05)
- 15 ± 5 minutes post injection
- 60 ± 15 minutes post injection
- 180 ± 15 minutes post injection
- 18-20 hours post injection

Use of an intravenous catheter is not required for PK blood sampling. If an IV catheter is used, at least 3 mL of blood must be drawn and discarded prior to collecting the PK blood sample. Blood samples will be collected in 5.5 mL heparinized vacutainer tubes.

Radioactivity in approximately 2 mL of whole blood will be quantitated in a calibrated well counter and decay corrected to the time of study drug administration. The radioactivity in urine will be obtained from cumulative quantitative planar imaging counts of the bladder wall obtained from radiation dosimetry.

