3 OVERVIEW OF METHODOLOGY AND DESIGN

3.1 Overall Study Design

Prospective, open-label, multicenter, dose escalation, and safety with PK and dosimetry study of injected Tc 99m tilmanocept in the detection of and assessment of localization to skeletal joints in subjects with and without active RA by SPECT imaging. Subjects will receive IV administration at one of 3 mass doses: 50 µg, 200 µg, or 400 µg. Within each mass dose group, subjects will receive Tc 99m tilmanocept labeled with one of 3 radiolabel doses: 1 mCi, 5 mCi, or 10 mCi. All subjects will have a whole body planar SPECT scan. Subjects enrolled in Groups 1-9 will receive a whole body planar SPECT scan and planar of hands at two specified time points: 60 minutes ± 15 minutes, and 180 minutes ± 15 minutes followed by a 3D SPECT or SPECT/CT scan on areas of interest. Subjects enrolled in Groups 10-11 will have a whole body planar SPECT scan with pharmacokinetic and dosimetry tests performed at 4 specified time points post injection: 15 ± 5 minutes, 60 ± 15 minutes, 180 ± 15 minutes, and 18-20 hours. Subjects enrolled in Groups 10-11 will also receive a planar SPECT hands scan at 60 ± 15 minutes and 180 ± 15 minutes post-injection. PK blood sampling will be performed before injection (within 15 minutes), immediately following injection (within 5 minutes), and at each scanning timepoint. Dosimetry tests will be performed at each scanning timepoint. PK of urine will be assessed through counts of the bladder wall obtained from cumulative quantitative planar imaging from radiation dosimetry. The proposed study includes 3 visits: A screening visit for initial determination of eligibility and evaluation of clinical status (Visit 1), a baseline: Day 1 (Visit 2) on the day of tilmanocept administration and imaging, and a safety follow-up (Visit 3).

The Schedule of Events ([Appendix 1](#)) contains a list of all study procedures and time points. Study activities are described in detail in [Section 7](#).

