8.3 SPECT/SPECT-CT Image Acquisition

The camera used to obtain the images should be a dual-headed SPECT or SPECT/CT camera equipped with a low-energy, high-resolution collimator with a 15% window (20% can be used if 15% setting not available) centered over a 140keV peak.

The camera must have passed the daily SPECT QC tests as per the manufacturer's recommendation for that day's scan schedule.

Whenever possible subjects should be asked to void after injection and prior to the first imaging session and again between imaging sessions.

Subjects should be positioned supine with arms at their side. The subject's head, legs, hands, and hips should be in the true anterior position. The subject should be instructed to remain as motionless as possible during the scan, and asked to breathe as shallowly as comfortable when the camera is passing over the chest. To help minimize leg motion, a light taping around the ankles can be used to keep the legs together. A pillow under the knees is often very helpful for comfort.

A whole body (head to toe) planar scan using auto-contour should be obtained at the following time points:

Groups 1-9 (see [Appendix 2](#)):

- 60 ± 15 minutes post administration
- 180 ± 15 minutes post administration

Groups 10-11 (see [Appendix 3](#)):

- 15 ± 5 minutes post administration
- 60 ± 15 minutes post administration
- 180 ± 15 minutes post administration
- 18-20 hours post administration

It is anticipated that the whole body scan would be acquired for 25-30 minutes. Using state-of-the-art 2-headed cameras (nominal 20" x 15" FOV) a target of 5-7 million counts should be obtained for the summed view of both heads. For the higher activity injections, it may be possible to attain this target in a shorter time, allowing the subject more time off the bed between scans.

A simple measure of the subject's "thickness" (i.e. from a lateral visual view, the height of the subject's anterior-most chest/abdomen above the scan bed) should be documented. This will be used for the attenuation correction to be applied to the anterior/posterior views obtained from the whole body scan.

Following the whole body acquisition, a planar image with both hands in the FOV should be acquired for ~ 5-7 minutes in both the anterior and posterior view for subjects in Groups 1-9 and subjects in Groups 10 and 11 at 60 ± 15 and 180 ± 15 minutes post-administration .

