9.3 Efficacy Variables

The efficacy variables for this study are as follows:

- Nuclear medicine specialist qualitative determination of presence/absence of radiotracer uptake (i.e., Tc 99m tilmanocept localization positive/negative) relative to background from SPECT imaging results for each DAS28 joint location for each subject (deemed the “gold standard” result, 28 joint locations per subject)
 - Clinically identified presence/absence of RA using the DAS28 instrument (28 joint locations per subject)
- Quantitative planar imaging intensity of radiotracer uptake for each joint location

A location/joint would be considered clinically identified as RA positive if it is either swollen or tender as measured by the DAS28 instrument. The presence of radiotracer uptake relative to background as determined by the nuclear medicine specialist at a location would indicate the location is RA positive.

The efficacy endpoints for this study are as follows:

- Per subject localization rate of Tc 99m tilmanocept by SPECT imaging
- Per joint location clinically RA-identified joint localization rate of Tc 99m tilmanocept by SPECT imaging

- Concordance of Tc 99m localization with anatomical areas of active RA defined by clinical symptomology.
- Localization intensity for each clinically RA-defined joint (as determined by quantitative SPECT gamma counts)
- Per subject localization rate of Tc 99m tilmanocept in areas other than RA-positive joints by SPECT imaging
- The following PK parameters will be calculated for each subject, whenever possible, using Tc 99m tilmanocept total radioactivity in whole blood and urine: maximum observed concentration (C_{max}), time to C_{max} (t_{max}), area under the concentration-time curve (AUC) from Hour 0 to the last measureable concentration (AUC_{0-t}), AUC extrapolated to infinity ($AUC_{0-\infty}$), apparent terminal elimination rate constant (λ_z), and apparent terminal elimination half-life ($t_{1/2}$).
- Radiation dosimetry of Tc 99m tilmanocept will include radiation doses per organ ($\mu\text{Gy}/\text{MBq}$), organs receiving the highest organ dose (HT), effective doses per organ ($\mu\text{Sv}/\text{MBq}$), mean effective dose ($\mu\text{Sv}/\text{MBq}$), effective dose resulting from a diagnostic dose $\pm 20\%$. Dosimetry will be based on target organ image counts and modeling per OLINDA/EXM® 2.0 software.

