9.5.4 Analysis of RPK and Dosimetry Variables

The RPK variables for Groups 10 and 11 are the whole blood and urine radioactivity levels per time point. The radioactivity in whole blood will be measured directly using the blood samples. The radioactivity of urine will be obtained from counts of the bladder wall obtained from radiation dosimetry. RPK parameters will be estimated for each subject using noncompartmental models. Summary statistics (n, mean, std, CV, geometric mean) will be computed for each RPK parameter across all subjects by Group (10, 11).

For dosimetry data, for each dosimetry parameter, summary statistics (n, mean, std, and a one standard deviation width confidence interval) will be computed by organ type and overall across all subjects by Group (10, 11). Analysis of Safety Variables

The number and percentage of subjects with any pharmacologic activity or ADRs will be tabulated by dose group and overall.

All adverse events (AEs) will be observed for each subject from the time of signing of informed consent until exit from the study. A treatment emergent adverse event is defined as an adverse event whose start date is on or after the procedure date. If the procedure date and/or the AE start date are missing, the AE will be considered treatment emergent.

Prior to analysis, all adverse events (AEs) will be coded using the MedDRA coding dictionary. Based on these coded terms, treatment emergent AEs will be summarized by dose group and overall as follows:

- by system organ class and preferred terms
- by system organ class and preferred terms and relation to study drug
- by system organ class and preferred terms and severity

Observed and change from baseline vital sign parameters, ECG parameters and hematology, clinical chemistry and urinalysis parameters will be summarized using descriptive statistics (mean, median, standard deviation, minimum, maximum and range) at each time point by dose group and overall.

Other safety analyses will be described in the Statistical Analysis Plan (SAP) for the study.

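### Urine PK for Groups 10-11 is read from bladder images while subjects are asked to void before and between them, so the planned urine parameters would reflect void timing

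*Combined protocol and SAP*

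**What the plan says.** - **Source of the urine data.** Section 8.4: "The radioactivity in urine will be obtained from cumulative quantitative planar imaging counts of the bladder wall". Section 9.5.4 names the same source without the word cumulative: "The radioactivity of urine will be obtained from counts of the bladder wall obtained from radiation dosimetry". The synopsis (study design) and Section 3.1 agree.
- **Voiding.** Section 8.3: "Whenever possible subjects should be asked to void after injection and prior to the first imaging session and again between imaging sessions". This stands ahead of the scan times for both Groups 1-9 and Groups 10-11, so it covers the PK groups.
- **Variable and method.** Section 9.5.4: "The RPK variables for Groups 10 and 11 are the whole blood and urine radioactivity levels per time point", and "RPK parameters will be estimated for each subject using noncompartmental models".
- **Parameters.** Section 9.3 and the synopsis list Cmax, tmax, AUC0-t, AUC0-∞, λz and half-life, to be calculated where possible "using Tc 99m tilmanocept total radioactivity in whole blood and urine".
- **Scan times, Groups 10-11.** Section 3.1: "4 specified time points post injection: 15 ± 5 minutes, 60 ± 15 minutes, 180 ± 15 minutes, and 18-20 hours".
- **What is absent.** Appendix 1 has no urine collection for radioactivity. Urinalysis in Table 2 is pH and specific gravity. No urine volume, void time or allowance for voided activity is described. Section 8.4 states decay correction for the blood counts only.

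**The concern.** Cumulative excretion at a given time is everything that has passed into urine by then, whether still in the bladder or already voided. A bladder image sees only the first part. Once a subject voids, that activity leaves the measure unrecorded, and the protocol asks for voids at the points where this does most harm.

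The parameters make it worse. A Cmax is a concentration, and image counts without a urine volume do not give one. λz and half-life need a declining curve, but bladder content declines only because of voids (or uncorrected decay). Summaries by group would then mix excretion with bathroom timing, with 6 subjects in each of Groups 10 and 11. Urine PK is a named secondary endpoint under the PK and dosimetry objective, so these numbers would be reported as findings.

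**Working it through.** The documents give no figure for urine PK, so there is nothing to reproduce. The check asks what the planned readings would show if true excretion were known.

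**Inputs from the documents.** Images at 15, 60 and 180 min and at 19 h = 1140 min (midpoint of 18-20 h). Tc 99m half-life 6.02 h (abbreviations list).

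**Assumptions.** Excretion is mono-exponential with half-time T = 60, 120 or 240 min. Each void empties the bladder fully. Counts are decay-corrected. The total excreted fraction cancels in the ratios and is set to 1.

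**Formulas.**
- True cumulative excretion: C(t) = 1 − 2^(−t/T).
- Bladder reading: B(t) = C(t) − C(time of last void).
- Recovery if the four readings are summed: ΣB / C(1140).
- Apparent half-life from the last two readings: ln 2 × 960 / ln[B(180)/B(1140)].

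**Worked case, T = 120 min.** True C is 0.083, 0.293, 0.646 and 0.999 at the four images.

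| Void pattern | B at 15, 60, 180, 1140 min | ΣB / C(1140) | tmax (min) | Apparent half-life |
|---|---|---|---|---|
| 10 min before each image | 0.0545, 0.0420, 0.0210, 0.0001 | 12% | 15 | 120 min |
| Midway (7.5, 37.5, 120, 660 min) | 0.0406, 0.0981, 0.1464, 0.0207 | 31% | 180 | 340 min |
| No voids | 0.083, 0.293, 0.646, 0.999 | 202% | 1140 | none (counts rise) |

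The underlying excretion is identical in all three rows. The first row returns the true half-life only because every reading covers the same 10-minute interval.

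**Recovery across T = 60, 120, 240 min.**

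| Void pattern | Sum of readings / true 19 h excretion |
|---|---|
| 10 min before each image | 18%, 12%, 7% |
| Midway between images | 35%, 31%, 31% |
| 30 min after images 1-3, no overnight void | 57%, 68%, 79% |
| 15 min after images 1-3, no overnight void | 77%, 84%, 89% |
| Immediately after images 1-3, no overnight void | 100%, 100%, 100% |
| No voids | 253%, 202%, 163% |

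Without voids each image already contains the earlier activity, so summing double-counts.

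**Decay.** An uncorrected count at 19 h keeps 2^(−19/6.02) = 0.11 of its time-zero value. If the silence on bladder counts means no correction, that is a further distortion.

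**Would whole-body loss alone repair it?** No. Whole-body retention still contains unvoided urine, so injected minus retained measures voided activity only. With midway voids it captures 51-52% of true excretion at 15 min and 72-86% at 180 min. Adding back B(t) from the same image gives [C(t) − B(t)] + B(t) = C(t), whatever the void times.

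**The case against.** The best reply is that the size is unknown and may be modest. Voiding is requested only where feasible. In Groups 10-11 the first 15 minutes are already filled by a PK draw, an ECG and vital signs, so an early void may often not happen. If subjects void just after each of the first three images and not overnight, the summed readings recover 57-100%. This stands: no single percentage can be put on the error.

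The counts are also said to come from the dosimetry work, which uses modelling software, and parameters are required only where calculable. A correction might exist in a procedure outside these documents. None is described, and Section 9.5.4 sends the per-time-point levels straight into noncompartmental estimation.

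Stronger readings are tempting but unsupported:

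- **A reader might infer that the plan must under-report urinary excretion.** It does so when activity is voided unseen. Summed readings without voids over-report.
- **A reader might infer that imaging the bladder wall misses the urine.** No region is defined, and a planar view over the bladder cannot separate wall from content. The term may be just an organ label.
- **A reader might infer that urine is known to be the major route here.** That statement is in Section 1.3.1, on nonclinical subcutaneous work. No human intravenous excretion split is given.

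**Conclusion.** The point holds and the rule is wrong as written, beyond a missing detail. Sections 8.3, 8.4, 9.3 and 9.5.4, followed together, produce urine parameters governed by void timing, and no estimable λz or half-life if nobody voids. A urine Cmax is undefined without a volume.

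That an error exists follows from the text. Its size does not: the range of 7% to 253% rests on assumed half-times of 1 to 4 hours, complete emptying and the void patterns listed. It illustrates sensitivity and does not predict the result.

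The consequence is limited to a descriptive secondary endpoint in 12 subjects. It should be corrected, but it does not threaten the trial's main conclusions.

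**What to change.** In Sections 8.4, 9.3 and 9.5.4, with matching edits to the synopsis and Section 3.1:

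1. Drop Cmax, tmax, both AUCs, λz and half-life for urine. Keep them for whole blood.
2. Report instead, for each subject in Groups 10-11 at each of the four whole-body scans: percent excreted = 100 × (injected activity − decay-corrected whole-body retention + decay-corrected bladder-region activity from the same image) / injected activity.
3. Take 100% as the measured injected activity, or as the first image where no void came before it. The assigned activity will not do, since Section 5.2 allows ±20% around it.
4. Record void times, which show whether the first image can serve as the 100% reference.
5. State that the whole-body and bladder counts are decay-corrected to the time of injection.

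The cost is wording, a bladder region drawn on images already acquired, and a void-time field in the case report form. No scan or sample is added. The downside is that all whole-body loss is attributed to urine. The measure should therefore be labelled total excretion and read as an upper bound for urinary excretion.

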8.4.1 Sample Processing

Whole blood samples will be processed in a well counter immediately following collection.

8.5 Dosimetry

Gamma camera planar images will undergo dosimetry analysis of all target organs. Dosimetry will be based on target organ image counts and modeling per OLINDA/EXM®2.0 (Organ Level Internal Dose Assessment/EXponential Modeling) software supplied by Hermes Medical Solutions (<https://www.hermesmedical.com/products/oncology-dosimetry-olinda-theranostics/>).

8.6 Safety

8.6.1 Adverse Events

8.6.1.1 Definition of Adverse Event

The definitions below follow International Conference on Harmonization (ICH) – Good Clinical Practice (GCP) (see also ICH Guideline for Clinical Safety Data Management: Definitions and Standards for Expedited Reporting).

Adverse Event (AE)

An AE is defined as any untoward medical occurrence in a subject administered a pharmaceutical product and which does not necessarily have a causal relationship with this treatment. An AE can therefore be any unfavorable and unintended sign (including an abnormal laboratory finding), symptom, or disease temporally associated with the use of a medicinal (investigational) product, whether or not considered related to the medicinal (investigational) product.

Any clinically significant change in a condition (worsening) from screening that results in a change in subject management will be considered an AE and will be recorded on the AE page of the CRF.

By definition for this study, all untoward medical occurrences beginning on the day of Visit 2 Baseline (Day 1) through the assessment of Visit 3 Follow-up () are to be reported as AEs. AEs continuing after study completion will be followed to normalization or stabilization. Additionally, untoward medical events occurring prior to the day of Tc 99m tilmanocept administration will be collect and added to the subject's medical history unless they are related to a study procedure in which case the event will be recorded as an AE. SAEs will be reported from the time of consent through the end of participation.

8.6.1.2 Categories for Adverse Event Assessment

All AEs will be assessed and documented by the investigator according to the categories detailed below.

Seriousness

For each AE, the seriousness must be determined according to the criteria given in [Section 8.6.1.5](#).

Severity

The severity of an AE is classified according to the following categories, taking into account the possible range of the intensity of the event:

- Mild - The adverse event is transient and easily tolerated by the subject.
- Moderate - The adverse event causes the subject discomfort and interrupts the subject's usual activities
- Severe - The adverse event causes considerable interference with the subject's usual activities and may be incapacitating or life-threatening.

Specific drug treatment

Any specific drug treatment will be documented.

Causal relationship to investigational product

The investigator will use the following definitions to assess the relationship of the adverse event to the use of investigational product:

Definitely related: Event can be fully explained by administration of the investigational product.

Probably related: Event is most likely to be explained by administration of the investigational product rather than the subject's clinical state or other agents/therapies.

Possibly related: Event may be explained by administration of the investigational product or by the subject's clinical state or other agents/therapies.

Probably not related: Event is most likely to be explained by the subject's clinical state or other agents/therapies, rather than the investigational product.

Definitely not related: Event can be fully explained by the subject's clinical state or other agents/therapies.

For causality assessments, events meeting the categories of definitely, probably, or possibly related will be considered to be related to investigational product.

Causal relationship to study procedure

The investigator will use the following definitions to assess the relationship of the adverse event to study procedure:

- Definitely related:** Event can be fully explained by the study procedure.
- Probably related:** Event is most likely to be explained by the study rather than the subject's clinical state or other agents/therapies.
- Possibly related:** Event may be explained by the study procedure or by the subject's clinical state or other agents/therapies.
- Probably not related:** Event is most likely to be explained by the subject's clinical state or other agents/therapies, rather than the study procedure.
- Definitely not related:** Event can be fully explained by the subject's clinical state or other agents/therapies.

For causality assessments, events meeting the categories of definitely, probably, or possibly related will be considered to be related to study.

8.6.1.3 Assessments and Documentation of Adverse Events

Attention shall be paid to the occurrence of AEs for the duration of subject participation. Events occurring prior to Visit 2 (day of Tc 99m tilmanocept administration) will be recorded in the subject's medical history. Untoward medical events beginning on Visit 2 (day of Tc 99m tilmanocept administration) through the completion of the Visit 3 Follow-up will be reported as adverse events. Thus, subjects should be closely observed by the investigator both during and after the evaluation.

Any AE (observed, volunteered, or elicited) should be recorded in detail in the source documentation.

The following information is required:

- The **date and time of onset** of any AE.
- The duration (the entire duration of an event or symptom, calculated from date of onset to date of end, if not recorded directly).
- The seriousness of the AE will be assessed by the investigator. If the investigator deems that an AE qualifies as an SAE, a special form provided by the sponsor should be completed and the event must be immediately reported to the sponsor. A definition of serious adverse events is provided in [Section 8.6.1.5](#).
- The maximum intensity (mild, moderate, or severe).
- Whether drug treatment was administered for the event, any specific drug treatment must be documented.

- The relationship of the AE to the investigational product and to study conduct (for definitions, see above).
The **outcome** of the AE (resolved, resolved with sequelae, not resolved, unknown, death).

AEs will be coded according to an internationally recognized dictionary (Medical Dictionary for Regulatory Activities [MedDRA]).

